9.5.2 Analyses with multiple imputation

The imputations will be carried out using the method of unrestricted random sampling with replacement (seed = 68686) and with 1,000 multiple imputed datasets created. It means that observed data is "bootstrapped" or sampled with replacement within the strata defined in the rows of Table 5, Table 6 and Table 7 and used to substitute (impute) missing data. If the actual significance level of the performed test will be between 4%-6%, then the number of imputations will be increased from 1,000 to 10,000. This will be done to ensure the precision of estimated standard error, and thus the right hypothesis testing conclusion will be made.

Statistical analysis plan Trial ID: SU-G-01	Date: Version:	27-Oct-2023 1.0		
EudraCT No.: 2020-000455-12	Status:	Final		
CONFIDENTIAL	Page:	40 of 47		

Missing data for each year will be imputed based on observed cases for the same year and using subjects as source for the imputations which happen to have data in the "current" year in question.

Further, PGPS data will be imputed from observed PGPS data and EGPS from EGPS data from the corresponding year and ongoing asthma status. The ongoing asthma status might only be considered if there is enough unique permutation to impute from.

The relevant endpoints in 1st and 2nd years will be analysed using a MMRM with treatment and year interaction, and ongoing asthma status as fixed effects and country and year interaction as random class effect and allowing unequal R-matrices among the two treatment arms. After the by-imputation MMRMs, results are summaries/combined using Rubin's method (**Rubin 1987**).

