15.11.1 Estimator

The main estimator and sensitivity estimator(s) for both estimands will be based on an identical method of statistical analysis (specified below), although the actual data used in each analysis may vary according to the different strategies taken for the handling of IEs and missing data. Further details of the different strategies for each estimand are provided in Sections **15.11.2** ,**15.11.3** and **15.14**.

Missing data will be imputed using the method of unrestricted random sampling with replacement. The average score will be imputed, but not the daily/weekly values. Missing data for 1st year will be imputed from observed data in 1st year and missing data for 2nd year will be imputed from the observed data in 2nd year. Thus, PGPS data will be imputed from observed PGPS data and EGPS from EGPS. Missing data for subjects with asthma will be imputed from patients with asthma

Clinical trial protocol	Date:	12-Nov-2021	× 1 1/
Trial ID: SU-G-01	Version:	4.0	
EudraCT No. 2020-000455-12	Status:	Final	
CONFIDENTIAL	Page:	62 of 77	

according the rules defined below and missing data for subjects without asthma will be imputed from subjects without asthma also following the rules defined below. Rubin's multiple imputation strategy with 1000 imputations will be used (**Rubin D.B 1987**). Seed used for imputation will be 12345.

The endpoints will be analysed using Mixed Model of Repeated Measurements (MMRM) assuming unequal variances in the two treatment groups. Each endpoint (TCS, RQLQ, DMS, DSS) is modelled over two seasons (2022 and 2023) for PGPS. Similarly, each endpoint is modelled over two seasons for EGPS. The summary of response variables analysis using MMRM is presented in Table 11.

Analysis number	Endpoint in 1st year	Endpoint in 2nd year
1	2nd key secondary endpoint: TCS during 1st PGPS	Primary endpoint: TCS during 2nd PGPS
2	3rd key secondary endpoint: average weekly overall RQLQ 1st PGPS	1st key secondary endpoint: average weekly overall RQLQ 2nd PGPS
3	Supportive secondary endpoint: average weekly overall RQLQ 1st EGPS	Supportive secondary endpoint: average weekly overall RQLQ 2nd EGPS
4	Supportive secondary endpoint: TCS 1st EGPS	Supportive secondary endpoint: TCS 2nd EGPS
5	Supportive secondary endpoint: DSS 1st PGPS	Supportive secondary endpoint: DSS 2nd PGPS
6	Supportive secondary endpoint: DSS 1st EGPS	Supportive secondary endpoint: DSS 2nd EGPS

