4.1 Multiplicity adjustment

The trial product estimand is the primary estimand for all endpoints. The analyses for the primary and for the three key secondary endpoints will be controlled for multiplicity to ensure a family wise type I error rate is no larger than 5%.

The multiplicity will be controlled by employing a hierarchical testing procedure by prespecifying the order of the hypothesis to be tested. For the primary and key secondary endpoints the null hypothesis tested, is the hypothesis no difference between placebo and 5grass mix SLIT-drops treatment group.

The testing order of hypothesis is:

- 1. The primary efficacy analysis of the average daily allergic rhinoconjunctivitis TCS during the 2nd PGPS.
- 2. The key secondary efficacy analysis of average weekly overall RQLQ score during the 2nd PGPS.

Statistical analysis plan	Date:	27-Oct-2023	
Trial ID: SU-G-01	Version:	1.0	
EudraCT No.: 2020-000455-12	Status:	Final	
CONFIDENTIAL	Page:	16 of 47	

- 3. The key secondary efficacy analysis of average daily allergic rhinoconjunctivitis TCS during the 1st PGPS.
- 4. The key secondary efficacy analysis of average weekly overall RQLQ score during the 1st PGPS.

The primary endpoint is the 1st hypothesis in the hierarchy and will be tested on a 5% significance level. The testing of endpoints from the 2nd to the 4th in the hypothesis hierarchy will only be is only carried out formally if all previously tested hypotheses are statistically significant at the 5% level.

Additional endpoints and analyses are supportive in nature, thus they will not be controlled for multiplicity.

5 Analysis sets

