6.1 General considerations

The efficacy data will be analyzed using estimand framework. The primary and first key secondary endpoints will be analyzed based on on-treatment (DPS1) and in-trial (DPS2) data, while the rest of the endpoints will be analyzed based on on-treatment (DPS1) data. Different approaches of handling missing data will be applied. Overview of analysis methods and analysis sets to be used are summarized in **Error! Reference source not found.**

Table 4 Summary of analyses

Enapoint	Analysis methods	Analysis sets	Data type
	Trial product estimand – main approach		Imputed, DPS1
	Trial product estimand – sensitivity analysis		
	Treatment policy estimand – main approach		Imputed DBS2
	Treatment policy estimand – sensitivity analysis		
Primary endpoint:TCS during 2 nd PGPS	Supportive analysis: Tipping- point analysis under the trial estimand – main approach	FAS	
Key secondary enpoind: RQLQ during 2 nd PGPS	Supplementary analysis: Ongoing asthma subgroup analysis		Imputed, DPS1
	Supplementary analysis: Subjects from the same household		
	Supplementary analysis: Symptoms-score tertiles analysis		Observed, DPS1
	Descriptive analysis	FAS/AAS	
	Trial product estimand – main approach		Imputed DPS1
Key secondary enpoind:	Trial product estimand – sensitivity analysis		
TCS during 1 st EGPS RQLQ during 1 st EGPS	Treatment policy estimand – main approach	FAS	Imputed DPS1
	Treatment policy estimand – sensitivity analysis		
	Descriptive analysis		Observed, DPS1
Secondary endpoints:	Trial product estimand – main approach	FAS	Imputed, DPS1
	Descriptive analysis		Observed, DPS1
Secondary endpoints:	Descriptive analysis	SAF	Observed

Unless otherwise mentioned all the statistical tests described in this section will use a significance level of 5% and all tests and confidence intervals will be two-sided. All null hypotheses are "*no differences in means between treatment arms*" and the alternative hypotheses will always be "*a (not specified) difference*".

Descriptive statistics for efficacy endpoints will be based on observed on-treatment data. Descriptive statistics for numerical (continuous) variables include displaying treatment group mean, SD, median, minimum and maximum. Descriptive statistics for categorical variables will include frequency tables displaying the numbers and percentages.

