The power calculations were done in two steps. This sample size wasthen evaluated using the estimand framework. The power was calculated for both the primary endpoint (TCS) and the key secondary endpoint (RQLQ). It is expected that the treatment difference in overall RQLQ during peak season is greater than the MCID of 0.10 and during entire season greater than 0.22 (Blaiss et al. 2022).

TCS power calculation

The estimated TCS mean, standard deviation and treatment differences during the peak season from three trials is presented in Table 8. The power calculation is based on a TCS treatment difference of 21% (1.64 in absolute value) and a common standard deviation of 5.5. Under these assumptions, the trial has a power of 80% with the sample size of 180 evaluable subjects. The power is 86% for the primary estimand and 80% for the secondary estimand with the assumption that 10% out of 220 subjects will discontinue the trial, with 4.5% of subjects discontinuing due to AEs and 1% due to lack of efficacy each year.

Trial	Placebo $\mu(\sigma)$	Active $\mu(\sigma)$	Difference absolute (relative)
GT-08 2006	8.44 (5.48)	5.14 (4.06)	3.3 (39%)
P05238	7.74 (6.50)	6.10 (5.09)	1.64 (21%)
P08067	5.73 (5.03)	4.56 (4.60)	1.17 (20%)
Average			2.04

Table 8: Mean and standard deviation of TCS during the peak of a season.

RQLQ power evaluation

The estimated RQLQ mean, standard deviation and treatment differences during the peak season from 3 trials raw data is presented in Table 9 below.

Table 9: Mean and standard deviation of RQLQ during the peak of a season.

Trial	Placebo $\mu(\sigma)$	Active $\mu(\sigma)$	Difference Absolute (relative)
GT-08 2005	1.82 (1.11)	1.37 (0.97)	0.45 (25%)
GT-08 2006	1.48 (1.05)	1.05 (0.91)	0.43 (29%)
P05238	1.73 (1.34)	1.41 (1.12)	0.33 (18%)
P08067	1.73 (1.34)	1.18 (1.08)	0.15 (11%)
Average	0.34		

A common standard deviation of 1.15 has been assumed in the power evaluation. An expected placebo mean is 1.60 and an expected treatment difference is 0.34. With 180 evaluable

Statistical analysis plan
Trial ID: SU-G-01
EudraCT No.: 2020-000455-12
CONFIDENTIAL

subjects per treatment arm, the power of 98% is reached for testing if RQLQ treatment difference is greater than proposed MCID of 0.1. The power is 95% for the primary and 92% secondary estimands for the sample size of 220 subjects with the same discontinuation assumptions as for TCS.

Conclusion

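### Imputed averages are drawn straight from a fixed donor pool, so the donors' own sampling error is left out and the 5% limit is not assured for the trial product estimand

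*SAP*

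**What the plan says.** SAP 9.5.2 replaces a missing seasonal average by one chosen at random from the observed averages, which are "sampled with replacement within the strata defined in the rows of Table 5, Table 6 and Table 7". This is repeated 1,000 times, the MMRM is fitted to each completed data set, and the results are combined by Rubin's rules. Protocol 15.11.1 plans the same: "Missing data will be imputed using the method of unrestricted random sampling with replacement". Neither text describes a step that redraws the donors, or the parameters of their distribution, before values are drawn.

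The donors depend on the estimand. For the trial product estimand (SAP 6.2.1, Table 5), active subjects who stop for lack of efficacy receive placebo values, and all other gaps are filled from the subject's own arm. For the treatment policy estimand (SAP 6.2.3, Table 7), active subjects who stop for IMP-related AEs also receive placebo values. Ongoing asthma status is matched throughout.

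SAP 4.1 wants the primary and key secondary analyses "controlled for multiplicity to ensure a family wise type I error rate is no larger than 5" per cent. SAP 9.5.2 goes to 10,000 imputations when the result falls between 4% and 6%, and explains: "This will be done to ensure the precision of estimated standard error, and thus the right hypothesis testing conclusion will be made".

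**The concern.** Rubin's rules give a valid variance only if each imputed data set also reflects uncertainty about the distribution from which the values come. Here that distribution is the same in all 1,000 data sets. The between-imputation variance then measures only the luck of the draw. It does not measure how far the donor mean itself might have differed in another sample.

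This touches the confirmatory test and its confidence interval. The step to 10,000 imputations reduces Monte Carlo noise and leaves the omission untouched. The planned sensitivity and tipping-point analyses would not reveal it: they change the donors or add a penalty but keep the same draw and pooling.

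**Working it through.** **Inputs.** SAP 6.1 sets the tests at two-sided 5%. SAP 7 gives difference 1.64, SD 5.5, 180 evaluable and 220 randomised per arm. It describes discontinuation both as 10% of 220 and as 10% per year, with 1% for lack of efficacy and 4.5% for AEs. I use both readings:
- 10% in total
- 1 - 0.9^2 = 19% by the second season

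Let f be the share missing per arm and g the share of the active arm filled from placebo. At the planned mix:
- Trial product estimand: g = 1%, or 0.1 x 19% = 1.9%.
- Treatment policy estimand: g = 5.5%, or 0.55 x 19% = 10.45%.

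**The plan's own figure.** With 180 per arm, 1.64 / (5.5 x sqrt(2/180)) = 1.64/0.580 = 2.83, which gives 80.8% power. The plan says "the trial has a power of 80% with the sample size of 180 evaluable subjects", so the inputs are read correctly.

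**Variance that Rubin's rules report** (N per arm, SD s, many imputations). The within part is 2s^2/N and the between part is 2fs^2/N. The total is (2s^2/N)(1+f).

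**Variance the estimator has under the null.** Averaged over draws, the filled active mean is (1-g) times the active donor mean plus g times the placebo donor mean. The filled placebo mean is the placebo donor mean. The difference is (1-g) times the difference in donor means, with variance (1-g)^2 (2s^2/N)/(1-f).

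**Ratio.** Rubin/true variance = (1-f^2)/(1-g)^2, and type I error = 2(1 - Phi(1.96 x sqrt(ratio))). With own-arm donors only (g = 0) the ratio is 1-f^2. At f = 19% the reported SE is 5.5 x sqrt(2 x 1.19/220) = 0.572, while the true SE is 5.5 x sqrt(2/(220 x 0.81)) = 0.583.

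| Case | f | g | Rubin/true SE | Type I, formula | Simulated |
|---|---|---|---|---|---|
| Nothing missing | 0 | 0 | 1.000 | 5.0% | 5.07% |
| Own-arm donors only | 10% | 0 | 0.995 | 5.1% | 5.25% |
| Own-arm donors only | 19% | 0 | 0.982 | 5.4% | 5.59% |
| Trial product, planned mix | 10% | 1% | 1.005 | 4.9% | 4.97% |
| Trial product, planned mix | 19% | 1.9% | 1.001 | 5.0% | 5.07% |
| Trial product, half that g | 19% | 0.95% | 0.991 | 5.2% | 5.36% |
| Treatment policy | 10% | 5.5% | 1.053 | 3.9% | 3.96% |
| Treatment policy | 19% | 10.45% | 1.096 | 3.2% | 3.33% |

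The simulations used 220 per arm and 200,000 null trials per case (100,000 for treatment policy). The Monte Carlo error at 200,000 is sqrt(0.05 x 0.95/200,000) = 0.05 points. The 5.07% with nothing missing is the baseline for the other rows.

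**How g is determined.** SAP 6.1.2 takes lack of efficacy only from the End of study form; the list of treatment-stop reasons has no such entry. Someone who stops IMP because it does not work but stays in the trial, as Protocol 5.1 encourages, is therefore classed under other reasons and given own-arm donors. A value of g below plan is plausible.

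**After redrawing the donors.** With own-arm donors the between part gains f^2/(1-f) x 2s^2/N, and the total becomes (2s^2/N)/(1-f), which is the true variance. The SE goes from 0.5500 to 0.5528 at 10% missing (+0.5%) and from 0.5721 to 0.5827 at 19% (+1.9%). With placebo donors the SE ratio is about 1/(1-g). Type I error is then 5.0% at g = 0, 4.8% at g = 1% and 4.6% at g = 1.9%. Simulation at 19% missing (10,000 trials, Monte Carlo error about 0.2 points) gave 5.2% at g = 0 and 4.8% at g = 1.9%.

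**The case against.** The strongest reply is that the plan's own inputs produce no excess. A reader might infer that the primary standard error is too small and that the 5% limit is exceeded. The documents do not support this. The f term is of second order and the g term of first order, so even 1-2% of the active arm filled from placebo cancels the omission.

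A reader might also infer that the omission is larger than the Monte Carlo error that SAP 9.5.2 guards against. With own-arm donors only, it moves z = 1.96 by about 0.036 at 19% missing, against a Monte Carlo SD of sqrt(0.19/(1.19 x 1,000)) = 0.013. At the planned mix the shift is only 0.002-0.01, and in the conservative direction. That inference fails too.

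Other points on this side also stand:
- Missingness may be lower than the discontinuation rate. SAP 6.2 needs only one observation for an average, and in SAP 6.2.5 a subject who stops treatment during the peak still counts as observed.
- For the first-season key secondary endpoints only about one year of loss applies, so 5.1% is the worst case there.
- Missing shares well above 19% have no basis in the documents.
- Redrawing the donors for the treatment policy estimand would widen a standard error that is already too large.

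What does not stand is the offset as a safeguard. Two errors cancel at one particular mix of reasons, and the validity of the test then depends on how many active subjects are coded to one category.

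**Conclusion.** The imputation as described is improper, and more imputations cannot repair it. For the trial product estimand, type I error is about 4.9-5.0% at the planned lack-of-efficacy share, about 5.2% at half that share with 19% missing, and about 5.1-5.4% with none. The limit in SAP 4.1 is not assured; the documents do not show that it is broken. For the treatment policy estimand Rubin's standard error is 5-10% too large and type I error about 3-4%, if nobody who stops provides later diary data.

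The effect is small, but it concerns the confirmatory test and the repair is nearly free. The result rests on equal missingness in both arms and on a pool of everyone observed in that season. The simulation used a single-season linear model in place of the two-season MMRM, normal scores and an assumed 30% with asthma. Adding an assumed 5% between-country share of variance, with own-arm donors only, gave 5.08% at 10% missing and 5.47% at 19%. The SAS code in Appendix A is not visible, so the reading relies on the text of SAP 9.5.2.

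**What to change.** In SAP 9.5.2, for the trial product estimand analyses, add an approximate Bayesian bootstrap step. For each imputed data set and each cell, first draw with replacement a donor set of the same size as the observed one, then draw the imputed values with replacement from that set. Keep the cells and Rubin's rules. Leave the treatment policy analyses as they are, since the step would only add to their conservatism.

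The cost is one sentence and one extra resampling call per cell. Own-arm standard errors become about 0.5-2% larger, and type I error falls slightly below 5%, to about 4.6-4.8%, at the planned lack-of-efficacy share. The sensitivity analysis of this estimand also takes IMP-related AE stops from placebo. By the same formula it is already conservative, and the step would make it slightly more so.

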15.14 Handling of missing data

Efficacy endpoints which are an average of daily diary entries over a defined pollen season period will be derived provided there is at least one relevant diary entry for that endpoint in the given pollen season period. Subjects with missing data for an endpoint will be included in the analysis of that endpoint through multiple imputation (see Sections 15.11.2, 15.11.3 and 15.11.4). Detailed specification of sensitivity analyses to address the assumptions underlying the main estimators of each estimand will be provided in the SAP.

Imputation of missing daily diary data is not considered for the main estimators of the trial product and treatment policy estimands. Occasional missing diary values are assumed to be missing completely at random (MCAR) and are therefore not a source of bias in the derivation of the endpoints. Investigation of patterns of extended periods of missing daily diary data and potential sensitivity analyses, however, will be considered in the SAP although appropriate imputation of missing daily diary values is a complex problem. Diary entries over the course of a pollen season are highly specific to the subject completing the diary; they are a function of the local pollen exposure in the immediate environment of the subject and that individual subject's tolerance to allergic rhinoconjunctivitis symptoms and subsequent rescue medication usage. Imputation of missing daily data could easily introduce daily data inconsistent with a subject's individual profile and subsequent bias in the derivation of the endpoints.

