Under the primary estimand, the assumption is that subjects who discontinue IMP due to "lack of efficacy" would not have experienced a treatment benefit other than that observed in the placebo arm. Contrary, subjects discontinuing for either of the two other reasons would have experienced a treatment benefit similar to the observed among subjects randomised to the same treatment arm.

These considerations imply that under the primary estimand, the only observed data used for analysis are obtained before discontinuation of IMP, while data obtained after discontinuation will be treated as missing. It further follows that imputation of missing data or data treated as missing will condition on the reason for discontinuation as outlined above. Moreover, data can be missing even for subjects not discontinuing IMP (e.g. due to low compliance). The reasoning for this type of missingness is ignorable and, consequently, this missing data will be imputed under the assumption that subjects experience a treatment benefit similar to that observed among subjects randomised to the same treatment arm. For further details, see section 6.2.1.

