6.2.1 Handling of intercurrent events and missing data for the trial product estimand – main approach

The relevant endpoints will be compared between treatment groups using the trial product estimand with population FAS and data point DPS1. This means that subjects for whom the endpoint is missing (the exclusion of daily diary data due to discontinuation of trial treatment) will still be included in the analysis through multiple imputations under the hypothetical situation where subjects continued to take trial treatment as planned. The missing data imputation is done using the following rules:

• For subjects that discontinue trial treatment due to lack of efficacy, multiple imputation of the missing endpoint will be taken from the placebo group. This assumes that had the subject continued to take trial treatment, they would have experienced similar efficacy to subjects in the placebo arm. Data are assumed to be missing not at random (MNAR).

Statistical analysis plan Trial ID: SU-G-01 EudraCT No.: 2020-000455-12 CONFIDENTIAL	Date: Version: Status: Page:	27-Oct-2023 1.0 Final 22 of 47		
---	---------------------------------------	---	--	--

- For subjects that discontinue trial treatment due to IMP-related AEs, multiple imputation of the missing endpoint will be taken from their own treatment group. This assumes that the level of efficacy that would have been experienced by the subject if they had continued to take trial treatment is unrelated to the occurrence of the AE and, if they had continued to take trial treatment, they would have experienced similar efficacy to subjects in their own treatment group irrespective to randomised treatment. Data is assumed to be missing at random (MAR).
- For subjects that discontinue trial treatment due to any other non-IMP-related reason or subjects that have missing data but completed the trial, multiple imputation of the missing endpoint will be from their own treatment group. This assumes that the level of efficacy that would have been experienced by the subject had they continued to take trial treatment is not related to their discontinuation of trial treatment. Data is assumed to be MAR.

In summary, missing data is imputed based on the following observed on-treatment data (Table 5):

Table 5: Sources of observed data used for imputation under the primary estimand.

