- The pattern of missingness (and consequently the pattern of imputation) may differ within the same subject for EGPS and PGPS. This pattern is (for each endpoint/pollen season) either:
 - Completely missing (both years 2022 and 2023 are missing)
 - Observed in 2022 but missing in 2023 (monotone missing pattern)
 - Missing in 2022 and observed in 2023 (this can happen if diary data is, in fact, missing during, the relatively short PGPS (2 weeks) in 2022 but the subject otherwise completed the trial and treatment) (not monotone missing pattern)
- "Completer" is a subject that is observed during both years.
- The number of observations upon which a subject's observed (EGPS and PGPS) average data depend considerably among subjects.

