The suggested sample size is 180 evaluable subjects per treatment arm. 220 subjects should be randomised in each arm, assuming a 10% discontinuation of subjects per year, where 1% discontinued due to lack of efficacy and 4.5% due to AEs. In such case, the trial has a power of at least 80% in order to detect a statistically significant difference of at least 21% with common standard deviation no larger than 5.5 for primary endpoint in observed case scenario. The trial has a power of 86% and 80% for primary endpoint for primary and secondary estimands respectively. Similarly, 95% and 92 % power for RQLQ for the primary and secondary estimand 0.1 in RQLQ for observed case.

8 Demographics and baseline characteristics

Summaries for numerical variables tables will display the descriptive statistics such as: mean, SD, median, min and max.

Summaries for categorical variables frequency tables will display counts and percentages.

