9.5.3 Model checking

The assumption of normally distributed residuals will be evaluated by visual inspection of quantile-quantile plots for the primary and key secondary endpoints. If the square root transformation does not result in a good approximation to the normal distribution, no transformation will be applied if this improves the approximation to a normal distribution.

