9.5.8 Convergence issues

If any models defined above do not converge, several attempts will be made to reach convergence:

- The first step will be set the same R-matrice among the two treatment arms.
- The second step will be to change the unstructured covariance matrix to the compound symmetry matrix.
- The third step we will be to remove ongoing asthma status from the model.
- The fourth step we will be to be to pool countries into regions.
- The fifth step will be to remove the random effect of region and year interaction from the model.

10 References

ICH 2020: ICH E9 (R1) addendum on estimands and sensitivity analysis in clinical trials to the guideline on statistical principles for clinical trials EMA/CHMP/ICH/436221/2017.

Chang et al. 2019: Chang, E. M., Gillespie, E. F., & Shaverdian, N. (2019). Truthfulness in patient-reported outcomes: factors affecting patients' responses and impact on data quality. Patient related outcome measures, 10, 171–186. https://doi.org/10.2147/PROM.S178344.

Juniper et al. 1998: Juniper, E. F., Howland, W. C., Robertsa, N. B., Thompson, A. K., & King, D. R. (1998). Measuring quality of life in children with rhinoconjunctivitis. Journal of allergy and clinical immunology, 101(2), 163-170.

Rubin 1987: Rubin, D.B. (1987) Multiple Imputation for Nonresponse in Surveys. John Wiley & Sons Inc., New York. http://dx.doi.org/10.1002/9780470316696.

Blaiss et al. 2022: Blaiss, M. S., Gronskyte Juhl, R., Siew, L. Q., Hammerby, E., & Devillier, P. (2022). Determining the minimal important differences in the RQLQ score with grass and tree allergy immunotherapy versus placebo in adults with moderate-to-severe allergy. Allergy, 77(6), 1843-1851.

 Date:
 27-Oct-2023

 Version:
 1.0

 Status:
 Final

 Page:
 43 of 47

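### Own-arm imputation of a missing 2nd-season average ignores the subject's 1st-season average, so the primary estimate is biased if the seasons correlate and score-related stopping, or its rate, differs by arm

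*SAP*

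**What the plan says.** SAP 6.2, 6.2.1, Table 5 and 9.5.2 define the imputation for the trial product estimand. Season averages are imputed, not daily values. Values are sampled with replacement within the table rows, which hold randomised arm, discontinuation reason and ongoing asthma status. Year and season type (peak or entire) are matched as well: "Missing data for each year will be imputed based on observed cases for the same year" (9.5.2). Protocol 15.11.1 has the same same-year rule. SAP 9.5.2 adds that asthma status may be dropped from the matching if too few donors are available.

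The rows *IMP-related AEs*, *Other* and *Data is missing* draw from the subject's own arm. *Lack of efficacy* draws from placebo. The assumption is declared. SAP 3.1.1.2 says that subjects in the first two of these rows "would have experienced a treatment benefit similar to the observed among subjects randomised to the same treatment arm". For other stops, SAP 6.2.1 says that the efficacy they would have had "had they continued to take trial treatment is not related to their discontinuation of trial treatment. Data is assumed to be MAR".

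SAP 6.2.5 lists subjects observed in 2022 and missing in 2023 as an expected pattern. The completed datasets go to a two-season MMRM, and the results are pooled by Rubin's rules.

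**The concern.** For a subject who completed the 1st season and then stopped, the 1st-season average is the best available information on the missing 2nd-season value. The plan collects it and then sets it aside. A donor matched only on arm, asthma status and year represents such a subject only if stopping has nothing to do with the 1st-season score.

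The documents give some reason to doubt this. Protocol 15.14 declines to impute daily values because "Diary entries over the course of a pollen season are highly specific to the subject completing the diary". The convergence plan in SAP 9.5.8 would "change the unstructured covariance matrix to the compound symmetry matrix", so the analysis model starts by letting the two seasons correlate freely. Under SAP 6.1.2 a stop counts as lack of efficacy only if the subject withdraws from the trial and that reason is noted on the end-of-study form; the treatment-stop form has no such option. Someone who stops treatment after a bad first season but stays in the trial, or who withdraws consent, falls under *Other* and gets an own-arm draw.

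The MMRM does not repair this, because every dataset it sees is already complete. No planned sensitivity analysis conditions on season 1. They change the donor arm (6.2.2, 6.2.4) or add a penalty to imputed active values (6.2.7.1). At stake is the estimate at the top of the testing hierarchy.

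**Working it through.** **1. The plan's own figures.** SAP 7 gives a difference of 1.64, SD 5.5, two-sided 5%, 220 per arm, "assuming a 10% discontinuation of subjects per year, where 1% discontinued due to lack of efficacy and 4.5% due to AEs".
- 180 per arm: SE = 5.5 × √(2/180) = 0.580; 1.64/0.580 − 1.96 = 0.87; power 80.8% (stated 80%).
- 220 per arm, SE = 5.5 × √(2/220) = 0.524. With the effect diluted by 2% (lack of efficacy over two years), power is 86.5% (stated 86%). With 11% dilution (lack of efficacy plus adverse events over two years), it is 79.5% (stated 80%).

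The planning inputs are therefore read correctly.

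**2. What the MMRM adds.** On one completed dataset, the year-2 contrast from a two-season GLS fit was −1.3311, and the asthma-adjusted raw year-2 difference was also −1.3311. Season 1 adds nothing once the gaps are filled.

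**3. Large-sample bias.** Let z be the standardised 1st-season score, b the log-odds of stopping per SD of z, p the proportion stopping after season 1, and ρ the between-season correlation. If all missing values come from own-arm stayers, the completed arm mean equals the stayers' mean, so

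arm bias = ρ × 5.5 × m_stay, with m_stay = −p/(1−p) × (mean z of stoppers).

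| b | p | mean z, stoppers | m_stay |
|---|---|---|---|
| 0.5 | 0.10 | 0.440 | −0.0488 |
| 1 | 0.05 | 0.895 | −0.0471 |
| 1 | 0.08 | 0.846 | −0.0736 |
| 1 | 0.10 | 0.817 | −0.0908 |
| 1 | 0.12 | 0.790 | −0.1077 |
| 1 | 0.15 | 0.751 | −0.1326 |

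The bias in the treatment difference is ρ × 5.5 × (gap in m_stay between arms). Both ρ and b are assumptions. Absolute values in TCS points:

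| Case | ρ = 0.2 | ρ = 0.4 | ρ = 0.6 |
|---|---|---|---|
| Equal b, equal p | 0 | 0 | 0 |
| b 1 v 0.5, p 10% each | 0.05 | 0.09 | 0.14 |
| b 0.5 v 0, p 10% each | 0.05 | 0.11 | 0.16 |
| b 1 v 0, p 10% each | 0.10 | 0.20 | 0.30 |
| b 1 in both, p 12% v 8% | 0.04 | 0.07 | 0.11 |
| b 1 in both, p 15% v 5% | 0.09 | 0.19 | 0.28 |

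Example: b 1 v 0.5 at ρ = 0.4 gives 2.2 × (0.0908 − 0.0488) = 0.09.

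**4. Fuller set-up, ρ = 0.4 / 0.6.** Here 10% stop at random before season 1 and 10% of the rest after it. Reasons are split 1 : 4.5 : 4.5, and lack-of-efficacy stops are drawn from placebo.
- b 1 v 0.5: 0.091 / 0.134.
- b 0.5 in active only: 0.109 / 0.157.
- b 1 in active, *Other* stops only: 0.086 / 0.133.
- b 1 in active, all stops: 0.194 / 0.298.
- Same rule on the raw score in both arms: 0.013 / 0.023 (b 0.5) and 0.044 / 0.067 (b 1), against the product.
- With conditional imputation in the own-arm rows, the residual bias is at most 0.012 in the moderate cases and 0.027 in the worst.

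**5. Simulated tests (6,000 runs, ρ 0.4-0.6).**
- No true effect, dependence stronger in active: two-sided rejection 5.1-6.1% (moderate) and 6.4-9.0% (b 1 in active only).
- True difference 1.64, dependence stronger in placebo: power 73-76% (b 1 v 0.5) and 62-70% (b 1 in placebo only), against 79% with conditional imputation.
- Stopping at random: 79.4% as planned, 79.2% with conditional imputation.

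**6. Against the tipping point.** By season 2, 1 − 0.9 × 0.9 = 19% are imputed. A bias of 0.09-0.16 corresponds to 0.09/0.19 = 0.47 to 0.16/0.19 = 0.84 points per imputed value, or one to two of the planned 0.5-point steps.

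**The case against.** The trial is double-blind with a matched placebo, so the natural expectation is that subjects in both arms stop by the same rule on what they experience. That case gives only 0.01-0.07 points, against the product. Bias towards the product needs dependence or stopping rates that differ by arm, and no document shows either. This stands, and it is why the point is conditional. It is not a full answer: with dependence in both arms, unequal stopping rates alone leave a bias, and an active product can cause stops that placebo does not.

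The evidence for correlation is thin. Protocol 15.14 speaks of entries within one season and ties them to local pollen, SAP 6.2 says that pollen varies by year, and an unstructured covariance says nothing about its size. This also stands, and it is why the range extends down to 0.2.

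The rule is prespecified in the protocol, its assumption is declared, and the tipping-point analysis partly covers bias in favour of the product. That analysis does not correct the estimate, however, and cannot reveal bias against the product.

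Two practical objections also have weight. A season average can rest on a single diary entry (SAP 6.2), so the covariate will be noisy for some subjects. The last visit was on 22-Sep-2023 and the SAP is dated 27-Oct-2023, so changing the confirmatory rule is a late step.

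**Conclusion.** The concern holds in conditional form. The own-arm draw requires stopping to be unrelated to the 1st-season score within arm and asthma status, a stronger condition than MAR given the data collected. The primary estimate is biased if the seasons correlate and either the dependence or the stopping rate (with some dependence) differs between arms. Equal dependence gives no bias only when stopping rates are also equal.

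The size rests on assumptions that the documents do not supply. With 10% stopping per year in each arm, moderate asymmetry gives about 0.05 TCS points at correlation 0.2 and 0.09-0.16 at 0.4-0.6, or 3-10% of 1.64. Log-odds of 1 in one arm only gives 0.10, and 0.19-0.30 respectively. Equal log-odds of 1 with unequal rates gives 0.04-0.11 (12% v 8%) or 0.09-0.28 (15% v 5%) over correlations 0.2-0.6.

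Three stronger readings are not supported:
- A reader might infer that the plan favours the product. The direction is unknown, and every asymmetric case here is hypothetical.
- A reader might infer a materially inflated false-positive rate. Marked inflation needs strong dependence confined to one arm, or running in opposite directions in the two arms.
- A reader might set the simulated 79% against the stated 86% and conclude that the trial is underpowered. The simulated figures only compare imputation methods under their own set-up; they do not replace the SAP's 86%.

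This should be changed because the correcting variable is already collected and the cost is small, not because a large bias has been shown.

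**What to change.** Before unblinding:
- In the Table 5 rows *IMP-related AEs*, *Other* and *Data is missing*, in both arms, impute the 2nd-season average conditional on the observed 1st-season average, within arm and with asthma status as a covariate. Predictive mean matching with parameter draws is one suitable method. It returns observed donor values, so it serves either scale allowed by SAP 9.5.3 ("If the square root transformation does not result in a good approximation to the normal distribution, no transformation will be applied" if that fits better). Where season 1 is also missing, draw it first as planned.
- Leave the lack-of-efficacy rows and the planned sensitivity analyses unchanged. Keep the planned unconditional draw as a sensitivity analysis.
- If the treatment policy estimand is changed too, condition only its *Other* and *Data is missing* rows, in both arms. Conditioning every placebo row but not the active rows drawn from placebo would create a shift towards the product of 0.05-0.16 points under equal dependence (log-odds 1 in both arms, 50-100% of stops without a 2nd-season diary), where the planned draw has none.
- State MAR as given arm, asthma status and 1st-season average. List the change in SAP 6.5 as a departure from protocol 15.11.1.
- Tabulate stopping rates, and the 1st-season TCS of stoppers and stayers, by arm.

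If the confirmatory rule can no longer be changed, add the conditional imputation as a prespecified sensitivity analysis for the primary and first key secondary endpoints.

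Minor: Table 5 takes donors with both years complete, Tables 6 and 7 allow either or both, and 6.2 and 9.5.2 admit partially observed subjects. One wording should be used throughout. With monotone dropout the 2nd-season donors are the same; only 1st-season draws and subjects missing 2022 but observed in 2023 are affected.

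Cost: SAP text, modest programming and one documented departure. No new data are needed, and about 0.2 percentage points of simulated power are lost if stopping is random.
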